9.5. Tanner Stage

The number and percentage of subjects in each Tanner Stage will be summarized by visit. The descriptive summaries will be repeated according to sex (ie, female vs male) and age groups at Day 1 [REDACTED]

9.6. Vital Signs, Weight and BMI

The vital signs data, including weight, BMI, blood pressure, body temperature, and heart rate (including orthostatic values, calculated as standing value minus supine value), will be summarized with descriptive statistics by visit. Observed and change from baseline values will be presented.

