Study population: Up to approximately 24 male and female subjects who meet all of the inclusion and none of the exclusion criteria may participate in this study. Eligible subjects who participated in Study NBI-827104-CSWS2010 aged 4 to 12 years (inclusive) at the time of enrollment in Study NBI-827104-CSWS2010 may enroll directly or indirectly into this study.

Subjects who did not participate in Study-NBI 827104-CSWS2010 may enroll if ██████████; these new subjects will be aged 4 to 12 years (inclusive) at the time of enrollment in Study NBI-827104-CSWS2025.

Duration of study treatment and study participation: The maximum duration of study participation for each subject is up to approximately 242 weeks, including up to 234 weeks of study treatment.

Investigational product, dosage, and mode of administration: NBI-827104 oral granules for sprinkle will be provided as ██████████ for oral administration to be taken qd ██████████.

Reference therapy, dose, and mode of administration: Not applicable

Endpoints

Primary (Safety):

- The occurrence of serious treatment-emergent adverse events (TEAEs).

Statistical methods:

[figure not shown]
Summary of safety analyses

Subject incidence of TEAEs, serious TEAEs, TEAEs leading to discontinuation of study treatment, and fatal TEAEs will be summarized by system organ class and preferred term.

Descriptive statistics will be generated for additional safety data, including clinical laboratory analytes (hematology and clinical chemistry, including thyroid function studies), vital signs, body weight, electrocardiogram parameters, and Children's C-SSRS.

[REDACTED]
 [REDACTED]
 [REDACTED]
 [REDACTED]

Plasma NBI-827104 concentrations will be summarized by DL and timepoint overall and by body weight category using arithmetic mean, minimum (min), median, maximum (max), SD, standard error (SE), and two-sided 95% CI of the mean.

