 - Long-Term Treatment Period C [REDACTED], if applicable: For subjects who exit Long-Term Treatment Period B to escalate to DL 5. Dose escalation to DL 5 will depend on evaluation of safety, tolerability, [REDACTED] of subjects who escalate to DL 4.
- Dose Taper Period [REDACTED]
- Safety Follow-Up Period [REDACTED]

The maximum duration of an individual subject's study participation is up to 242 weeks.

NBI-827104 will be administered orally qd during the Dose Titration, Long-Term Treatment, and Dose Taper Periods, for a maximum treatment duration of 234 weeks. Study visits will occur approximately every [REDACTED] during the first [REDACTED] of the study and the first [REDACTED] after dose escalation to DL 4 and DL 5. Thereafter, study visits will occur every [REDACTED], with phone calls approximately [REDACTED] after each study visit. At the end of their final Long-Term Treatment Period (A, B, or C), subjects will begin the Taper Period, followed by the Safety Follow-Up Period. Study visits are shown [Figure 1](#) and in the Schedules of Assessments in [Table 10](#) and [Table 11](#).

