8.2. Withdrawal from Study

If a subject prematurely withdraws from the study, the investigator will record the reason for withdrawal on the relevant eCRF. All subjects who withdraw from the study prematurely will be asked to have all ET assessments performed as soon as feasible and, unless consent has been withdrawn, will be asked to have a Safety Follow-Up phone call and visit approximately 1 week and 4 weeks after the last dose of study treatment, respectively. If a subject's last dose of study treatment was >1 week before the ET Visit, no additional phone call is needed; if a subject's last dose of study treatment was >4 weeks before the ET Visit, no additional visit is needed.

Reasons for withdrawal from the study include, but are not limited to:

- Withdrawal by the subject or parent(s)/legal guardian(s)
- AE
- Death

- Lost to follow-up
- Site terminated by Sponsor
- Study terminated by Sponsor
- Protocol deviation
- Investigator decision
- Sponsor decision

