9.3.3. Physical and Neurological Examination Including Height/Length and Tanner Staging

The complete physical examination will consist of an assessment of general appearance, extremities, skin and mucosae, head, eyes, ears, nose, throat, neck (including thyroid), lymph nodes, chest, lungs, cardiovascular, abdomen, genito-urinary, musculoskeletal, and neurological system, including assessment of level of consciousness, mental status, muscle strength and tone, coordination and gait, [REDACTED]

Height/length will be measured with subjects not wearing shoes. Height may be optional if the subject is unable to stand. If the investigator is unable to obtain height/length, the reason for noncollection must be captured in the eCRF. The physical examination schedule is provided in Table 10 and Table 11.

Physical signs of puberty will be assessed using Tanner staging as appropriate based on subject age and stage of puberty as part of the physical examination.

9.3.4. [REDACTED]

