3. STUDY DESIGN

This is a Phase 2, multicenter, open-label extension, interventional study to evaluate the long-term safety, tolerability, [REDACTED] of NBI-827104 in pediatric subjects with EECSWS. Eligible subjects may enroll directly following completion of the Week 12 study visit at the end of the maintenance period of Study-NBI-827104-CSWS2010 (known as CSWS2010 hereafter) or after a gap following completion of that study. Subjects who did not participate in CSWS2010 may enroll if [REDACTED]. This study is expected to enroll approximately 24 subjects aged 4 to 12 years (inclusive).

The study will consist of the following periods: a Screening Period [REDACTED], which is applicable only for subjects who do not enroll directly from or did not participate in CSWS2010; a Dose Titration Period [REDACTED]; a Long-Term Treatment Period [REDACTED]; a Dose Taper Period [REDACTED]; a Safety Follow-up Period [REDACTED]. The maximum duration of an individual subject's study participation is up to 242 weeks. For subjects who enroll directly from CSWS2010, the CSWS2025 Day 1 Visit is the same as the CSWS2010 Day 84/Week 12 (End of Maintenance) Visit. Assessments completed as part of the End of Maintenance Visit in CSWS2010 will be transferred to the CSWS2025 Day 1 electronic case report form (eCRF).

A complete Schedule of Assessments is provided in the study protocol.

Screening Period: For subjects who enroll directly from CSWS2010, informed consent/assent may be provided within 28 days prior to Day 1 or on Day 1. Subjects who do not enroll directly or did not participate in CSWS2010 must be provided with informed consent/assent before the start of screening assessments and will be screened to determine eligibility up to 28 days before the start of study treatment dosing on Day 1.

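### SAP 9.6 reports weight and BMI only in raw units and does not list height, so modest growth slowing or excess weight gain cannot be told from normal growth in the planned tables

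*SAP*

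**What the plan says.** The primary objective is long-term safety and tolerability in children. Subjects are 4 to 12 years old at entry to the parent study or, if new, to this one. About 24 are planned, in one open-label arm (SAP 3 and 3.1), and dosing continues "for a maximum treatment duration of 234 weeks" (Protocol 4.1).

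The relevant analysis is SAP 9.6. It names "The vital signs data, including weight, BMI, blood pressure, body temperature, and heart rate", adds orthostatic differences, and states: "Observed and change from baseline values will be presented". Under SAP 4.3.2, change is the later value minus the baseline value. The visible text gives no z-score, percentile, growth velocity or age and sex norm for any of these variables.

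Protocol 9.3.3 collects height: "Height/length will be measured with subjects not wearing shoes". A reason must be recorded when it cannot be obtained, and it can be skipped for a child who cannot stand. In the visible SAP, height is a baseline characteristic only (5.4). It is absent from the 9.6 list and from the list of safety measures that opens Section 9, which does name body weight and Tanner stage.

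Two nearby sections handle age differently. SAP 9.3 classifies laboratory values as low, normal or high, because several reference ranges apply, and sets aside raw values and changes for that reason. SAP 9.5 repeats the Tanner summaries by sex and age group.

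**The concern.** Children grow during the study whatever the drug does. With no control arm, nothing in the planned tables shows what the gain would have been without treatment. A mean change in weight or BMI then reflects normal growth, the age mix and who is still in the study at each visit, as well as any drug effect. The documents foresee growth, since both expect subjects to change weight group, but the analysis has no external yardstick for it.

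The risk is that a modest slowing of growth, or an excess weight gain, passes as an unremarkable increase. Height, the most direct measure of linear growth, would have no visible postbaseline summary at all.

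**Working it through.** **1. The plan's own durations.** Protocol 4.1: "The maximum duration of an individual subject's study participation is up to 242 weeks". The parts are screening "up to 28 days before the start of study treatment dosing on Day 1" (SAP 3), which is 28/7 = 4 weeks; treatment, 234 weeks; and follow-up. The planned length of follow-up is blacked out in Protocol 4.1.6, so I take 4 weeks from Protocol 8.2, which sets a "visit approximately 1 week and 4 weeks after the last dose of study treatment, respectively" for subjects who withdraw early.

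4 + 234 + 4 = 242 weeks, which reproduces the stated figure.

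In years, treatment is 234 × 7 / 365.25 = 4.48 and participation is 242 × 7 / 365.25 = 4.64. Both are maxima.

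**2. What raw change would look like.** The documents give no growth rates. I assume normal gains of 2 to 5 kg and 4 to 7 cm per year across these ages. Expected gain = rate × 4.48 × (1 − slowing), with the unrounded duration.

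| | Weight gain (kg) | Height gain (cm) |
|---|---|---|
| Normal growth | 9.0 to 22.4 | 17.9 to 31.4 |
| Slowed by 20% | 7.2 to 17.9 | 14.4 to 25.1 |
| Slowed by 50% | 4.5 to 11.2 | 9.0 to 15.7 |

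Weight gain 20% above normal gives 9.0 × 1.2 = 10.8 to 22.4 × 1.2 = 26.9 kg.

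For weight, every altered range overlaps the normal one. A gain of 15 kg fits normal growth, 20% slowing and 20% excess. For height, 20% slowing overlaps with normal and 50% slowing does not (15.7 is below 17.9), but that would help only if height were tabulated.

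**3. Does shorter follow-up change this?** No. The duration multiplies both ranges and cancels. At 20% slowing they overlap whenever 0.8 × the highest rate exceeds the lowest: 0.8 × 5 = 4.0 against 2 for weight, and 0.8 × 7 = 5.6 against 4 for height.

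**4. What standardizing gives.** On a z-score scale, the expected change under normal growth is about zero at any age. The 95% CI half-width for the mean change is t(0.975, n − 1) × SD / √n. The SD of z-score change is an assumption. I use n = 24 (planned total) and n = 12 (target for completing Week 12 at the highest dose level, Protocol 11.2).

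| Assumed SD | n = 24 | n = 12 |
|---|---|---|
| 0.3 | 0.13 | 0.19 |
| 0.5 | 0.21 | 0.32 |
| 0.7 | 0.30 | 0.44 |
| 1.0 | 0.42 | 0.64 |

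A mean shift of 0.5 z exceeds the half-width in all cases except SD 1.0 with n = 12. Attrition would widen these intervals.

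**The case against.** - **A growth effect would not be invisible.** A reader might infer that the plan cannot show any effect on growth. That goes too far. Observed weight and BMI are tabulated as well as change, BMI is built from height, and Tanner stage covers pubertal development. Weight loss or a gross shift in BMI would show. This stands, and the point is limited to modest effects.
- **Height may be summarized elsewhere.** The word that introduces the 9.6 list does not close it, parts of the SAP are blacked out, and the visit schedules are not shown. A postbaseline height output cannot be ruled out, so the documents do not support saying that none exists. Its absence from both visible lists makes one unlikely. Where BMI is available, a subject's height can be recovered as √(weight/BMI), but not from a table of means.
- **Z-scores do not isolate the drug.** This is correct. There is no control arm, and after an initial restricted period antiseizure drugs, ketogenic diet and steroids may be changed. A shift could come from these or from the disease.
- **Height will be missing for some children**, probably the most impaired. This stands and belongs in the fix.
- **Heart rate and blood pressure.** It is tempting to extend the point to them. The orthostatic differences are taken within a visit and are less exposed to age drift, the documents give nothing from which to size a problem, and age-specific limits would have to come from outside. They are not part of this point.
- **Priority.** The primary endpoint is serious TEAEs, and Protocol 11.5.2 promises only descriptive statistics here, which the SAP delivers. The data also stay in the database. This limits the severity, but the better summary is cheap and easier to defend if specified before lock.

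**Conclusion.** The point holds in its limited form. The planned weight and BMI summaries cannot separate modest growth slowing or excess weight gain from normal growth, and postbaseline height is missing from the visible lists. Under the assumed rates, the overlap for weight is wide: 9.0 to 22.4 kg with normal growth against 7.2 to 17.9 kg with growth slowed by 20%. The overlap does not depend on children reaching the 234-week maximum.

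This rests on growth rates and z-score SDs that are not in the documents, and on reading the visible lists as they stand. The overlap arises because normal gain differs by age. Knowing the actual age mix would narrow it, but only by comparison with an outside growth reference, which is what the plan lacks. No magnitude is claimed for BMI. It is a worthwhile correction to a secondary safety summary and does not touch the primary endpoint.

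**What to change.** In SAP 9.6:

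- Add height to the variables summarized by visit.
- Derive z-scores for height, weight and BMI by age and sex from a named published growth reference, and summarize the observed z-score and its change from baseline by visit.
- Count the subjects whose z-score falls or rises by preset amounts, for example at least 0.5 and at least 1.
- Report the number with missing height at each visit.
- State that, without a control arm and with later changes in concomitant treatment allowed, a z-score shift is a signal and not proof of a drug effect.

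Age-specific high and low flags for heart rate and blood pressure are an optional secondary addition.

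Age, sex, weight and, where obtainable, height are already collected. Protocol 11.5.2 leaves the detail of these summaries to the SAP, and SAP 1 places analysis decisions before database lock, so no protocol change is needed. The cost is one standard derivation and a few tables, with height and BMI z-scores missing for some subjects.

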9.7. Electrocardiogram

The triplicate ECG parameter values recorded at each timepoint for heart rate, PR interval, QRS duration, QT interval, and QTcF (corrected QT interval using Fridericia's formula) interval will be averaged (and rounded to the nearest whole number) for each subject and timepoint for the purpose of statistical summarization. Additionally, for the triplicate investigator overall categorical assessment (ie, Normal, Abnormal not Clinically Significant, or Abnormal Clinically Significant) at each timepoint, the outcome representing the greatest degree of abnormality will be selected for summarization.

Descriptive statistics for the observed values and change from baseline will be presented for each of the ECG parameters by timepoint.

Frequency tables (number and percentage of subjects) will be presented for the overall categorical assessment at each timepoint.

Two additional categorical summaries (frequency tables displaying number and percentage of subjects) will be presented for the QTcF interval. For the first summary, the observed QTcF values at each timepoint will be classified as follows:

- Greater than 450 msec
- Greater than 480 msec
- Greater than 500 msec

For the second categorical summary, the change from baseline to each subsequent timepoint will be classified as follows:

- Increase greater than 30 msec
- Increase greater than 60 msec

The same categorical summaries will be presented in frequency tables for values at any postdose timepoint (including unscheduled assessments) meeting the aforementioned criteria.

9.8. Columbia-Suicide Severity Rating Scale

The C-SSRS is a measure of suicidal ideation and behavior. The C-SSRS data will be presented in the following summaries:

Neurocrine Biosciences, Inc.
Statistical Analysis Plan

Study NBI-827104-CSWS2025
6 September 2024

- Screening/lifetime assessment: data will be summarized for subjects who did not enroll directly from CSWS2010.
- Baseline assessment
- Postbaseline assessments

Each summary will display the number and percentage of subjects who report “Yes” to specific C-SSRS items or categories of items (a category is assigned a “Yes” value if a “Yes” is reported for any item in the category). These C-SSRS items and categories are as follows:

- Suicidal Ideation Items
 - (1) Wish to be dead
 - (2) Non-specific active suicidal thoughts
 - (3) Active suicidal ideation with any methods (not plan) without intent to act
 - (4) Active suicidal ideation with some intent to act, without specific plan
 - (5) Active suicidal ideation with specific plan and intent
- Suicidal Ideation Category: Any of items (1) through (5)
- Suicidal Behavior Items
 - (6) Preparatory acts or behavior
 - (7) Aborted attempt
 - (8) Interrupted attempt
 - (9) Non-fatal suicide attempt
 - (10) Completed suicide (“Since Last Visit” assessments only)
- Suicidal Behavior Category: Any of items (6) through (10)
- Suicidal Ideation or Behavior Category: Any of items (1) through (10)

For the “all postbaseline assessments” summary, each subject’s C-SSRS responses for all postbaseline assessments will be evaluated, and a “Yes” response for any assessment will be considered as a “Yes” for the subject.

In addition to the summaries described above, shift tables comparing postbaseline suicidal ideation scores to baseline scores will be presented. The shift table scores are defined as the following:

- 0 = No suicidal ideation
- 1 = Wish to be dead
- 2 = Non-specific active suicidal thoughts
- 3 = Active suicidal ideation with any methods (not plan) without intent to act
- 4 = Active suicidal ideation with some intent to act, without specific plan
- 5 = Active suicidal ideation with specific plan and intent

The shift tables will display the number and percentage of subjects within each cell of a 6 x 6 table, with the rows representing the baseline score and the columns representing the maximum score recorded across all postbaseline assessments (including both scheduled and unscheduled visits). Subjects missing either a baseline score or all postbaseline scores will not appear in the table.

Neurocrine Biosciences, Inc.
Statistical Analysis Plan

Study NBI-827104-CSWS2025
6 September 2024

9.9. Prior and Concomitant Medications

Prior and concomitant medications will be summarized by WHO Drug Anatomical Therapeutic Chemical Classification (ATC) Level 3 category (or Level 2 if there is not an applicable Level 3 category) and preferred names. Medications from the antiseizure medication history eCRF page are assumed to be prior medications and imputation of dates will not be performed. Missing start and stop dates will be handled according to Section 4.3.5.2.

Medications will be summarized in frequency tables. The frequency tables will include the number and percentage of unique subjects reporting the medication one or more times. For medications, the table will be sorted alphabetically by ATC class and then, within an ATC class, by preferred names. Prior and concomitant medications are defined as mutually exclusive categories according to the first dose as follows:

■	[REDACTED]
	[REDACTED]
	[REDACTED]
■	[REDACTED]
■	[REDACTED]
	[REDACTED]
	[REDACTED]
■	[REDACTED]
	[REDACTED]
■	[REDACTED]
	[REDACTED]
	[REDACTED]

Neurocrine Biosciences, Inc.
Statistical Analysis Plan

Study NBI-827104-CSWS2025
6 September 2024

10. PERFORMANCE QUALIFICATION OF SAS® PROGRAMS

The analysis and summary of data from this study will be performed using SAS® 9.4 (or a later release if available). All SAS® programs used in the production of statistical analyses, tables, listings, and figures described in this SAP will undergo performance qualification (verification that the program produces the intended output) in accordance with department standard operating procedures. The performance qualification may include independent programming and/or peer review of the SAS® log files. In addition, tables, figures, listings, and statistical analysis output will be independently reviewed for completeness and accuracy.

-
- A horizontal bar chart titled "U.S. should take action to address climate change" showing the percentage of respondents who believe the U.S. should take action to address climate change, broken down by age group. The y-axis lists age groups: 18-29, 30-49, 50-69, 70+, and a combined group of 18-29, 30-49, 50-69, 70+. The x-axis represents the percentage from 0 to 100. The bars are black. The data is as follows:
- | Age Group | Percentage |
|--------------------------|------------|
| 18-29 | ~85% |
| 30-49 | ~80% |
| 50-69 | ~85% |
| 70+ | ~45% |
| 18-29, 30-49, 50-69, 70+ | ~95% |
| 18-29, 30-49, 50-69, 70+ | ~100% |
| 18-29, 30-49, 50-69, 70+ | ~95% |
| 18-29, 30-49, 50-69, 70+ | ~90% |
| 18-29, 30-49, 50-69, 70+ | ~95% |
| 18-29, 30-49, 50-69, 70+ | ~80% |
| 18-29, 30-49, 50-69, 70+ | ~95% |
| 18-29, 30-49, 50-69, 70+ | ~90% |
| 18-29, 30-49, 50-69, 70+ | ~45% |

Neurocrine Biosciences, Inc.
Statistical Analysis Plan

Study NBI-827104-CSWS2025
6 September 2024

